7.5 End of Study Treatment

The follow-up evaluations required after treatment ends due to completion of the planned study treatment period, disease progression, or once the patient is discontinued due to unacceptable toxicity or decision to discontinue treatment by the patient or the study physician are specified in Appendix D.

After withdrawal from or completion of protocol treatment, patients must be followed up for AEs for 30 calendar days after the last dose of study drug. The following assessments will be performed:

- Physical examination including measurement of weight
- Medical history
- Vital signs
- ECOG performance status
- AE assessment
- Concomitant medication review
- CBC, including 3-part differential and platelets
- CMP
- Serum or urine pregnancy test
- CT scans of chest, abdomen and pelvis, if no disease progression or not done within prior 6 weeks.

CONFIDENTIAL

7.6 Follow-up

7.6.1 Follow-up for Patients Who Discontinue Prior to Disease Progression

Patients who discontinue study treatment prior to the occurrence of disease progression will be followed every 3 months (± 1 month) from the date of last dose of study drug until disease progression. Tests to be performed are listed in Appendix D. Patients will not be followed up for survival if they start any subsequent therapy.

The following tests will be done during follow up visits:

- Medical history will be updated
- Physical examination, including weight and vital signs (includes blood pressure, heart rate, breathing rate, and oral temperature)
- CBC, including 3-part differential and platelets
- CMP
- 24-hour urine collection for 5-HIAA testing
- CT scan of the chest, a CT scan of the abdomen/pelvis .

8. DRUG FORMULATION, AVAILABILITY, ADMINISTRATION, AND TOXICITY INFORMATION

8.1 Carfilzomib

Carfilzomib is a synthetic small molecule peptide bearing the chemical name (2S)-N-((S)-1-((S)-4-methyl-1-((R)-2-methyloxiran-2-yl)-1-oxopentan-2-ylcarbamoyl)-2-phenylethyl)-2-((S)-2-(2-morpholinoacetamido)-4-phenylbutanamido)-4-methylpentanamide.

Investigational Product	Dosage Form and Strength	Manufacturer	
Carfilzomib	60 mg	Onyx Therapeutics, Inc.	

8.1.1 Labeling, Packaging, and Supply

Carfilzomib for Injection is supplied as a lyophilized parenteral product in single-use vials packaged in multi-vial cartons. Institutional pharmacies will be supplied with open stock vials with full-disclosure labels.

The immediate packaging will contain a statement to conform with U.S. Food and Drug Administration (FDA) Investigational New Drug (IND) requirements as follows: Caution: New Drug - Limited by Federal (or United States) law to investigational use.

CONFIDENTIAL

All study drugs must be kept in a secure place under appropriate storage conditions. Storage conditions for carfilzomib are included on the investigational product label.

SCRI Innovations must be granted access on reasonable request to check drug storage, dispensing procedures, and accountability records.

8.1.2 Preparation and Administration of Carfilzomib

For the purpose of this study, carfilzomib will be administered as an IV infusion over 30 minutes.

Preparation and administration instructions will be provided in the pharmacy instruction.

8.1.3 Infusion reaction

Infusion reactions associated with IV administration of carfilzomib were characterized by a spectrum of systemic symptoms including fever, chills, arthralgia, myalgia, facial flushing, facial edema, vomiting, weakness, shortness of breath, hypotension, syncope, chest tightness, or angina. These reactions can occur immediately or up to 24 hours after administration. Administration of dexamethasone prior to carfilzomib dosing reduce the incidence and severity of reactions. Inform patients of symptoms and ask them to contact physician if symptoms of an infusion reaction occur. Infusion reactions should be treated as per institutional protocol.

Infusion reactions (e.g., rash, urticaria, erythema, pruritus, bronchospasm, and hypotension) can occur with the agent used in this study. To identify the grade of a reaction, refer to the list below adapted from the General Disorders and Administration Site Conditions section of the NCI CTCAE v 4.03:

- Grade 1: Mild transient reaction; infusion interruption not indicated; intervention not indicated.
- Grade 2: Therapy or infusion interruption indicated but responds promptly to symptomatic treatment (e.g., antihistamines, NSAIDs, narcotics, IV fluids indicated for ≤24 hours).
- Grade 3: Prolonged (e.g., not rapidly responsive to symptomatic mediation and/or brief interruption of infusion); recurrence of symptoms following initial improvement; hospitalization indicated for other clinical sequelae. Note: any infusion that is interrupted and not resumed within the visit will be considered a Grade 3 reaction.
- Grade 4: Life-threatening consequences; urgent intervention indicated.

Minor symptoms such as flushing, skin reactions, dyspnoea, lower back pain, hypotension, or tachycardia may require temporary interruption of the infusion. However, severe reactions, such as hypotension requiring treatment, dyspnoea requiring bronchodilators, angioedema or generalized urticaria may require immediate treatment discontinuation and aggressive symptomatic therapy. Patients who experience a severe reaction should not be re-challenged.

CONFIDENTIAL

STUDY DRUG(S): CARFILZOMIB AMENDMENT 2 DATE: 25 FEBRUARY 2015

Patients who experience an allergic/infusion reaction may be pre-medicated for subsequent cycles per local guidelines and clinical practice.

8.1.4 Precautions and Risks Associated with Carfilzomib

Precautions and risks are located in the IB.

8.2 Accountability for All Study drugs

The Principal Investigator (or designee) is responsible for accountability of all used and unused study drug supplies at the site.

All study drug inventories must be made available for inspection by SCRI Innovations or its representatives and regulatory agency inspectors upon request.

At the end of the study, all SCRI Innovations Drug Accountability Record Form(s) will be completed by the site and sent to the SCRI Innovations Regulatory Department. Study drug supplies must not be destroyed unless prior approval has been granted by SCRI Innovations. Please contact SCRI Innovations regarding disposal of any study drug.

9. **RESPONSE EVALUATIONS AND MEASUREMENTS**

Response and progression will be evaluated in this study using the Response Evaluation Criteria in Solid Tumors (RECIST) Version 1.1 (see Appendix E). Lesions are either measurable or non-measurable according to the criteria. The term "evaluable" in reference to measurability will not be used, as it does not provide additional meaning or accuracy.

10. STATISTICAL CONSIDERATIONS

10.1 Statistical Design

This is a multicenter, Phase II study of carfilzomib for the treatment of patients with advanced neuroendocrine cancers.

Demographic data and baseline disease characteristics will be summarized using appropriate descriptive statistics (e.g., mean, median, standard deviation or percentages and frequency counts).

The primary endpoint, ORR, will be determined using RECIST v1.1 criteria. The median and 25% and 75% percentiles for PFS will be summarized with associated 95% CI, and the distribution of PFS will be presented graphically using the Kaplan-Meier approach. Progression-free survival will be evaluated six and 12 months after the last patient is enrolled on the trial.

10.2 Sample Size Considerations

This study will enroll up to 62 patients. Simon's optimal two-stage design (Simon, 1989) will be used for go/no go decision making. The null hypothesis that the true response rate is 0.05 will be *CONFIDENTIAL*

STUDY DRUG(S): CARFILZOMIB AMENDMENT 2 DATE: 25 FEBRUARY 2015

tested against a one-sided alternative. In the first stage, 23 patients will be accrued. If there is 1 or no response in these 23 patients, the study will be stopped. Otherwise, 33 additional patients will be accrued for a total of 56. The null hypothesis will be rejected if at least 6 responses are observed in 56 patients. This design yields a type I error rate of 0.05 and power of 80% when the true response rate is 0.15. The sample size will be increased by 10% to an accrual of 62 patients, to account for potential non-evaluability.

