10.4.1 Efficacy Analysis

Efficacy analyses will be reported for FAS population. Additionally, the ORR, Clinical Benefit Rate (CBR), and PFS will be summarized for the Evaluable Population. The following outcomes will be used to evaluate the clinical benefit of the study treatment:

- Overall Response Rate (ORR) is defined as the proportion of patients with confirmed complete response (CR) or partial response (PR (i.e. 2 CRs or PRs at least 4 weeks apart) according to RECIST v1.1 criteria.
- Clinical Benefit Rate (CBR) is defined as the proportion of patients with CR, PR or stable disease (SD) (≥ 6 cycles) according to RECIST v1.1 criteria.

CONFIDENTIAL

- For ORR and CBR, patients without a post-baseline tumor assessment will be classed as not evaluable (NE) and considered as non-responders.
- Progression-free Survival (PFS) is defined as the time from the first day of study drug administration (Day 1) to disease progression as defined by RECIST v1.1 criteria, or death on study. Patients who are alive and free from disease progression will be censored at the date of last tumor assessment.

For ORR and CBR, the estimates and the associated 95% CI based on the Clopper-Pearson method will be calculated. For PFS, Kaplan-Meier curves will be generated and the median time to event and the associated 95% CI be provided.

Safety Analysis

Safety will be assessed through the analysis of the reported incidence of treatment-emergent AEs. Treatment-emergent AEs are those with an onset on or after the initiation of therapy, and will be graded according to NCI CTCAE v4.03. A copy of CTCAE scoring system may be downloaded from: https://evs.nci.nih.gov/ftp1/CTCAE/CTCAE.

The AEs will be coded using Medical Dictionary for Regulatory Activities (MedDRA), and summarized using system organ class and preferred term for all patients in the Safety Population. In addition, summaries of serious adverse events (SAEs), AEs leading to treatment discontinuation, AEs by maximum NCI CTCAE grade, and AEs related to study treatment will also be presented.

Other safety endpoints including changes in laboratory results, vital signs and ECG findings will be summarized for the safety population. Summaries of laboratory abnormalities based on maximum CTCAE grading will also be produced.

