10.5.2 Planned Interim Analysis

No interim analyses are planned. Interim results may be presented at congress prior to final study report, if applicable. The design follows that of Simon et al. 1989. If < 2 of the initial 23 patients enrolled in the study fail to achieve a response, the study will be stopped and the remaining 33 additional patients will not be enrolled. Patients will be evaluated for response to treatment every 3 cycles. Patients will be removed from treatment at the time of disease progression. Patients demonstrating an extended period of stable disease will be considered non-responders after 12 cycles of treatment.

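### The 10% allowance for non-evaluable patients is added to the total but not to the stage-1 look, so power is about 0.77 rather than 0.80 if the allowance is used up and the first 23 enrolled are counted

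*Combined protocol and SAP*

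**What the plan says.** Section 10.2 (Sample Size Considerations) adopts a two-stage rule: "Simon's optimal two-stage design (Simon, 1989) will be used for go/no go decision making". The null response rate is 0.05 and the test is one-sided. For stage 1, "In the first stage, 23 patients will be accrued", and the study stops if there are 0 or 1 responses. Otherwise 33 more are accrued, for a total of 56, and the null is rejected with at least 6 responses. The claim is: "This design yields a type I error rate of 0.05 and power of 80% when the true response rate is 0.15". The section then ends: "The sample size will be increased by 10% to an accrual of 62 patients, to account for potential non-evaluability".

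Section 10.5.2 (Planned Interim Analysis) attaches the stopping rule to "the initial 23 patients enrolled in the study".

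For ORR, section 10.4.1 (Efficacy Analysis) says that "patients without a post-baseline tumor assessment will be classed as not evaluable (NE) and considered as non-responders".

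No section enlarges the stage-1 number, makes the look wait for 23 evaluable patients, or says how the 6 extra patients divide between the stages.

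**The concern.** The plan allows for some patients contributing no response information and adds 6 patients for them. Those 6 help only if the trial reaches stage 2. If the stage-1 rule counts the first 23 enrolled, with non-evaluable patients as non-responders, a 10% rate leaves about 23 × 0.9 = 20.7 informative patients at the look, yet 2 responses are still required.

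What is at stake is a wrong stop for an active drug. Stage 1 is the only early stopping point, and the extra patients cannot repair a wrong stop because they are never enrolled after one.

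**Working it through.** **Inputs.** From section 10.2: p0 = 0.05, p1 = 0.15, n1 = 23, stop at ≤1 response, n = 56, reject at ≥6, accrual raised to 62. From section 10.4.1: non-evaluable (NE) patients count as non-responders. Assumptions made here: 0.15 is the rate among evaluable patients, and non-evaluability occurs at random with probability d.

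**1. Reproduce the stated design.** With b(x; n, p) the binomial probability,

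P(reject) = Σ over x = 2 to 23 of b(x; 23, p) × P(Bin(33, p) ≥ 6 − x).

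- p = 0.05: 0.04996, the stated 0.05.
- p = 0.15: 0.8003, the stated 80%.
- A grid search returns the same design (1/23, 5/56) as Simon's optimal one.
- 56 × 1.10 = 61.6, rounded up to 62.

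The plan's figures are right when every patient is evaluable. At 0.8003 there is no slack.

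**2. Wrong stop at stage 1.** P(stop) = (1 − p)^23 + 23p(1 − p)^22.

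- All evaluable, p = 0.15: 0.0238 + 0.0966 = 0.1204.
- 10% NE counted as failures, p = 0.15 × 0.9 = 0.135: 0.0356 + 0.1278 = 0.1634.

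**3. Overall power, look at 23 enrolled, final rule on a full 56 evaluable.** Let M be the number evaluable among the first 23, with M ~ Bin(23, 1 − d). Stage 2 then supplies 56 − M evaluable patients, and the sum in step 1 is averaged over M.

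| NE rate d | Power at 0.15 | Type I error at 0.05 |
|---|---|---|
| 0 | 0.800 | 0.050 |
| 5% | 0.785 | 0.048 |
| 9.7% (6/62) | 0.768 | 0.046 |
| 10% | 0.767 | 0.046 |
| 15% | 0.746 | 0.044 |
| 20% | 0.722 | 0.042 |

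For fixed M, power is 0.788 with 22 evaluable at the look, 0.774 with 21 and 0.758 with 20.

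**4. Other reading of the final denominator.** With at least 6 responses among 62 enrolled and NE as failures, d = 10% gives power 0.765 and type I error 0.046. The shortfall at 10% is almost the same, so it arises at the stage-1 look and not from the final cut-off. On this reading type I error does depend on d (0.057 at 5%), so the statement that it is not inflated is limited to the 56-evaluable reading.

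**5. Look at 23 evaluable, final rule on 56 evaluable.** This is the calculation in step 1: power 0.800, type I error 0.050. Expected enrolment at the look is 23/0.9 = 25.6.

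**The case against.** The strongest reply is that 23, 33 and 56 are all Simon design numbers, and the 10% was added afterwards so that each is reached in evaluable patients. Section 10.2 uses the same verb for 23, 56 and 62. On that reading power is 0.800 as stated. The 0.767 figure, by contrast, needs about 56 − 20.7 = 35.3 evaluable patients in stage 2, where the plan says 33. The word enrolled comes only from section 10.5.2, in a loosely worded sentence that also implies a total of 23 + 33 = 56 enrolled rather than 62. This stands in part: section 10.2 alone is ambiguous. But the only text that resolves it says enrolled, nothing says evaluable, and anyone running the look from these sections would count the first 23 enrolled.

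A second reply is that 0.15 may already count NE patients as non-responders, as the ORR definition does. Then nothing is lost at stage 1. That reading would leave the plan's own inflation without a purpose, so it is the less likely one, but the power claim does not say which rate is meant.

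Third, 10% is an allowance for potential non-evaluability and not a forecast. This is right. At 5% the loss is 1.5 points, and one NE patient in stage 1 costs about 1.2.

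**Conclusion.** The point holds conditionally. If the stage-1 rule counts the first 23 enrolled, 0.15 is the rate among evaluable patients, and random non-evaluability reaches the full 10%, a wrong stop becomes about a third more likely (16.3% against 12.0%) and power is about 0.77, some 3 points below the stated figure. With the final rule on 56 evaluable patients, type I error falls slightly, to about 0.046.

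A reader might infer that the sample-size arithmetic is wrong, or that the trial has 77% power whatever happens. The documents support neither. The stated type I error, power and inflation all reproduce, and the shortfall depends on the three conditions above. The defect is that the plan does not carry its own allowance through to the stage-1 look or say which patients that look counts. This should be corrected, but it does not undermine the design.

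**What to change.** In sections 10.2 and 10.5.2, state that the stage-1 rule applies to the first 23 response-evaluable patients and the final rule to 56, within the existing cap of 62. About two or three of the 6 extra patients then fall in stage 1. This restores power 0.800 and type I error 0.050, provided 56 evaluable patients are reached. Since 62 × 0.9 = 55.8, the text should also say how the final rule is read if the cap yields slightly fewer.

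The term needs its own definition: a post-baseline tumor assessment, or progression or death before the first scan, counted as non-response so that early failures are not replaced. Distinguish it from the Evaluable Population in section 10.3, which requires two full cycles and no major violations. Align the NE wording in section 10.4.1, which at present classes every patient without a post-baseline assessment as NE.

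Do not substitute a look at a fixed 26 enrolled with at least 6 of 62. That gives type I error of 0.0503 at 10% NE and 0.062 at 5%. A fixed 25 enrolled gives power of only 0.790 at 10% NE on the same final rule.

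If the look stays at 23 enrolled, restate power as about 0.77 under 10% non-evaluability.

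The cost is two or three more patients before the stage-1 look, revised sentences in sections 10.2 and 10.5.2, one definition, and a matching edit in section 10.4.1. The cap of 62 does not change.

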10.3 Analysis Population

The following analysis populations will be used:

- The Full Analysis Set (FAS) will consist of all enrolled patients who receive at least one full or partial dose of study group and who have measurable disease at baseline.
- The Evaluable Population will consist of the subset of the FAS who receive at least 2 full cycles of study drug and who no major protocol violations or deviations.
- The Safety Population is defined as all patients who have received at least one full or partial dose of study treatment and for whom post baseline safety assessments are available.

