7.4 Response Assessment Every 3 Cycles

Patients will be evaluated for response to treatment after every 3 cycles of treatment. The following assessments will be performed:

- CT scans of chest, abdomen and pelvis (if abnormal at baseline)
- 24 hour urine for 5-HIAA

Patients with progressive disease or unacceptable toxicity should be discontinued from the study; patients with stable disease or response to therapy will continue treatment.

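### The additional Evaluable Population summaries select on completing two cycles while PFS runs from Day 1, so PFS, ORR and CBR in that set tend to be too favourable; the main FAS results are not affected

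*Combined protocol and SAP*

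**What the plan says.** Section 10.3 defines two efficacy sets. The FAS is "all enrolled patients who receive at least one full or partial dose of study group and who have measurable disease at baseline". The second set is narrower: "The Evaluable Population will consist of the subset of the FAS who receive at least 2 full cycles of study drug", with the further condition of no major protocol violations or deviations.

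Section 10.4.1 gives the FAS the leading role ("Efficacy analyses will be reported for FAS population") and then adds: "Additionally, the ORR, Clinical Benefit Rate (CBR), and PFS will be summarized for the Evaluable Population". PFS is "the time from the first day of study drug administration (Day 1) to disease progression" by RECIST, or death on study. For censoring, "Patients who are alive and free from disease progression will be censored at the date of last tumor assessment". The same definition serves both sets: no landmark, delayed entry or separate time origin is given for the Evaluable Population. For ORR and CBR, the section counts patients without a post-baseline tumour assessment as non-responders.

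Section 7.4 fixes the scan schedule: "Patients will be evaluated for response to treatment after every 3 cycles of treatment". Section 5 sets the cycle at 28 days, with dosing on days 1, 2, 8, 9, 15 and 16.

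**The concern.** Membership of the Evaluable Population is decided by what happens after treatment starts, but the PFS clock starts at treatment. A patient who dies during the first two cycles can never enter the set, and one who progresses and stops then cannot either. Everyone who does enter has the time up to qualification counted in the PFS, with almost no opportunity for an event during it. That is immortal-time bias.

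ORR and CBR face the same filter. A confirmed response needs two assessments at least four weeks apart, and stable disease counts towards CBR only from six cycles. The first scheduled scan follows Cycle 3, so patients who leave before completing two cycles are nearly all non-responders. Dropping them shrinks the denominator and hardly touches the numerator. It also bypasses the plan's own safeguard, because early stoppers are removed before the rule counting unassessed patients as non-responders can reach them.

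Nor does the criterion identify patients whose response was assessed. A patient can complete two cycles and have no post-baseline scan. An early stopper scanned at the end of treatment (Section 7.5) and found to have progressed is excluded.

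At stake is a second set of efficacy figures that looks better than the FAS for reasons of selection, with no caution in the plan about how to read it.

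**Working it through.** **The plan's own figure.** The only design calculation is for response (Section 10.2): stop at 1 or fewer of 23, reject at 6 or more of 56, response rates 0.05 against 0.15. The exact two-stage binomial gives type I error 0.04996 and power 0.8003, so the stated 0.05 and 80% reproduce. The 10% increase also reproduces: 56 × 1.1 = 61.6, rounded to 62. This neither supports nor weakens the point. No PFS target or power is stated.

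**Inputs for PFS.**
- Two cycles end at L = 2 × 28 = 56 days. The last Cycle 2 dose falls on day 28 + 16 = 44, which could also be read as having received two full cycles of drug. At 30.4375 days per month these are 1.84 and 1.45 months.
- First scheduled scan: 3 × 28 = day 84.
- Illustrative median PFS *m*: 5.5, 11.0 and 16.4 months, from the trials cited in Sections 1.2 and 1.4's preceding background (sunitinib trial control arm; everolimus arms of the pancreatic and carcinoid trials). These are assumptions.

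**Upper bound: exponential PFS, every event recorded when it occurs.** With S(t) = 2^(−t/m), the share excluded is 1 − S(L). Among those retained, survival from Day 1 is S(t)/S(L), and setting this to 0.5 gives a median of m + L. For m = 5.5 and L = 56 days, S(L) = 2^(−1.84/5.5) = 0.793, so 20.7% are excluded and 6-month PFS is 0.469/0.793 = 0.592.

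| m (months) | Excluded, L = 56 d | Evaluable median, L = 56 d | Evaluable median, L = 44 d | 6-month PFS, full set → Evaluable (L = 56 d) |
|---|---|---|---|---|
| 5.5 | 20.7% | 7.34 | 6.95 | 46.9% → 59.2% |
| 11.0 | 10.9% | 12.84 | 12.45 | 68.5% → 76.9% |
| 16.4 | 7.5% | 18.24 | 17.85 | 77.6% → 83.9% |

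**With the scan schedule.** Progression was placed on an 84-day grid, and a fraction *c* of events surfaced off schedule (death, clinical or unscheduled progression). The documents do not give c, so it was varied. Simulation of 400,000 patients per scenario, L = 56 days, 6-month PFS read at day 183:

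| m | c = 0 | c = 0.25: excluded; 6-month PFS | c = 0.5: excluded; 6-month PFS |
|---|---|---|---|
| 5.5 | no exclusion, no bias | 5.2%; 49.1% → 51.8% (+2.7) | 10.4%; 48.4% → 54.0% (+5.6) |
| 11.0 | no exclusion, no bias | 2.8%; 70.0% → 72.0% (+2.0) | 5.5%; 69.5% → 73.5% (+4.0) |
| 16.4 | no exclusion, no bias | 1.9%; 78.9% → 80.4% (+1.5) | 3.7%; 78.4% → 81.4% (+3.0) |

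No scenario gave a downward bias. The 6-month rate is the steadier measure here. On the grid, medians sit on scan dates and jump, and the three illustrative medians all happen to lie close to one (days 168, 336 and 504 are 5.52, 11.04 and 16.56 months). The model does not include toxicity withdrawals or treatment past progression.

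**ORR.** Six responders among 56 is 10.7%. If six early non-responders are dropped, 6/50 = 12.0%; if twelve, 6/44 = 13.6%. The numbers dropped are illustrative.

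**The case against.** The strongest reply is that the plan already protects the result that matters. The FAS is the main efficacy population, needs only one dose and measurable disease, and keeps every early failure. A reader will have an unfiltered figure beside each Evaluable one. This stands, and it limits the weight of the point.

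Some stronger readings are tempting but not supported:
- *The Evaluable median is inflated by 1.84 months (33% at a median of 5.5).* That needs every early event to be recorded when it occurs. The first scheduled scan comes after the two-cycle threshold, so before it mainly deaths and off-schedule progressions can be removed. The entry criteria (ECOG 0 or 1, life expectancy above 12 weeks) make many very early deaths unlikely.
- *Retained patients cannot have an event in the first eight weeks.* Section 3.3 lets some patients continue after progression, and the threshold could be met at day 44.
- *All three endpoints are shifted upward by construction.* The bar on major violations can also remove responders, and the effect on PFS of dropping toxicity withdrawals cannot be signed.
- *The bias carries into a comparison with historical medians.* Section 10 states no PFS benchmark, hypothesis or test. The published medians are background only.

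Section 5 names PFS as a primary endpoint while Sections 2.1 and 2.2 make it secondary. That needs reconciling, but the FAS leads either way.

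**Conclusion.** The point holds for the additional Evaluable summaries only. Their definition conditions on a post-baseline outcome, and their PFS keeps a Day 1 origin, so they tend to be too favourable. Confidence is high on the direction and low on the size. The PFS bias runs from zero (c = 0) through 1.5 to 5.6 points on 6-month PFS (c = 0.25 to 0.5) to the exponential upper bound on the median, and all of these rest on assumed medians and an assumed rate of off-schedule detection. The ORR and CBR effect depends less on scan timing and more on how many patients stop early, which the documents do not predict. The change should be made before analysis. A reader should not infer that the FAS results are compromised.

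**What to change.** In Section 10.4.1:
- Report PFS and CBR in the FAS only.
- If a supportive PFS is kept, make it a labelled landmark analysis: patients alive and progression-free at the end of Cycle 2, with time counted from that landmark. Under the exponential model this removes the added time, returning medians of 5.5, 11.0 and 16.4 months.
- For supportive ORR, define evaluable as having at least one post-baseline tumour assessment, or progression or death before one, with the latter counted as non-response. Amend Section 10.3 to match.

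A sentence calling the Evaluable PFS supportive and conditional on two cycles would help readers, but would leave the event-free time in the estimate.

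The change needs no extra patients, visits or data. The supportive figures become slightly less favourable, and a landmark PFS answers a conditional question and must be described as such.
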